Mailed letters: Potentially eligible patients (meeting the inclusion criteria) will receive a recruitment letter signed by the patient's provider as well as a brochure that describes the study and explains that they can call the study line if they are interested, or that a research assistant will call them in the next few weeks to find out if they might be interested in participating in the study. Patients who do NOT want to be contacted about the study will be asked to return an enclosed opt-out card to the study office within 4 days of receiving the brochure. The opt-out card (attached) will be generic in that it will not identify the potential participant by name, but rather will have a coded number assigned by the research team, and will not note any health information or UC Davis affiliation to ensure their privacy. In addition, it will provide a space for the individual to request that they not receive any additional solicitations for research participation by the institution. A research assistant will only call patients who have not returned the opt-out card within the stated time period (3-4 weeks after letters mailed). Patients who express an interest in the study will be contacted by study staff to discuss their participation and to set up an appointment to sign the consent and receive the technology training (either intervention or usual care). Consenting participants meeting eligibility will be randomized to either Care Coordination or the $P^2E^2T^2$ program.

Patient and Provider Engagement and Empowerment through Technology $(P^2E^2T^2)$ to Improve Health in Diabetes

Telephone Calls placed to potentially eligible participants: Research staff will screen patients for eligibility over the phone and set up an appointment to complete informed consent. Consenting participants meeting eligibility will be randomized to either Care Coordination or the $P^2E^2T^2$ program. Patients who provide an opt-out card for participating will not receive any telephone call inquiring about their interest in participating in the study.

Local recruitment: A study coordinator and/or nurse health coach from the study will work with clinic staff and providers to identify potential participants by reviewing physician appointment schedules. For these potentially eligible participants, recruitment and the consent process will be done in-person at the time of scheduled clinic appointments by CITI trained research staff or nurse coach with the provider's approval.

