Practice alerts: With the approval of clinics and providers participating in the study, the informatics team may initiate pop-up practice alerts when a potentially eligible patient is in the clinic for an appointment. If the patient meets pre-set guidelines (over 18 years of age, diagnosis of Type 2 diabetes), an electronic alert in the EHR will appear that this patient may be eligible for a UC Davis Research study for the provider to review. The provider has an option of ignoring this alert or may briefly discuss that the patient may be eligible for a study and inquire if the patient would like further information. If the person requests further information, the provider clicks a button that will send information to the study coordinator, so that a member of the research team can call the participant or meet with them in person to discuss the study.

Advertisements: Participants will be recruited between January and August, 2016 through advertisements/flyers placed at participating clinics at local health systems. The flyers will provide information and describe the study as a Technology Enabled Support Program for Patients with Diabetes.

Health Management and Education: Trained study personnel may also promote recruitment for the trial by attending and describing the study to participants during diabetes education classes conducted at the UC Davis Center for Health Management & Education. The study will be presented as described and advertisements/flyers will be distributed. When study personnel are present, potential participants will be given the option to sign up to receive further information about the study. Participants may also be recruited directly through referral by local providers or Advisory Board Members.

Randomization will be conducted through computer generated randomization using REDCap data management system. This randomization will occur immediately following consent by computer generated randomization programming in Redcap. The participant will then be assigned a study ID number which will be used to track all of their activity within the study (questionnaires, fitness tests, coaching sessions). Only the study ID #, no personal identifiers, will be included on any of these study documents.

Patient and Provider Engagement and Empowerment through Technology $(P^2E^2T^2)$ to Improve Health in Diabetes

Copies of recruitment flyers; provider letters; and informed consent documents are attached to this document.

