9) Compensation to the Subjects

All subjects, regardless of treatment arm, will be given a health monitoring device at the end of the study. Upon completion of study questionnaire and their regularly scheduled visit with their primary care physician all participants will receive \$50 at baseline, 3 and 9 months. Those participants in the intervention $(P^2E^2T^2)$ arm will receive a health monitoring device at the beginning of the study; and those participants in the Care Coordination arm of the study will also receive a health monitoring device upon successful completion of all study questionnaires. If participants do not complete all aspects of the study, they will not receive the health monitoring sensor device. Each sensor device is worth approximately \$75.

10) Study Timelines

Each individual will be enrolled in the study for 9 months. Each participant will complete a study questionnaire at baseline, 3 months and 9 months. Estimated duration of the study completion is 24 months from start of enrollment (January 1^{st} , 2016 – December 31^{st} , 2017).

11) Study Endpoints

Outcomes to be evaluated include: i) Quality of Life (QOL) measures; ii) Self-efficacy; iii) Readiness to Change; and iv) Clinically Relevant Indicators (HgbA1C, HDL, LDL, triglycerides). All measures will be collected in both groups at the study timelines. At baseline (time of recruitment), all participants will be asked to complete the surveys and the care coordinator will request the primary care provider orders for the laboratory tests measuring the clinical indicators. The lab tests are routinely used to monitor diabetes management and are typically covered by insurance. Should the patient not have a payment source for the laboratory assays, the project will cover the cost of the laboratory tests. At 3 months and 9 months, surveys links will be sent by email to each participant along with a reminder to complete the laboratory work ordered by their provider. If not completed, reminder emails or phone calls may be made by the study team. The primary endpoints of the study are: baseline data; data at the completion of five sessions of support calls during the 3 months of the intervention; and data at 6 months after the end of the intervention (9 months after baseline).

12) **Procedures Involved**

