Historical data, such as completed lab work values as identified above (Study Endpoints section), will be gathered by querying the EHR for all participants involved in the study. This will be accomplished by working with the Health Informatics for research group, led by [name].

All data and data identifiers related to this study will be destroyed seven years after completion of the study. All data findings from the study will be presented as aggregate data with no individual subject identifiers.

Subjects will be using commercial off-the-shelf (COTS) sensors, smart phone applications, and web-based physical activity dashboard technologies. Participants must agree to use the sensors and applications required for data collection. If they are unwilling to use this sensor, they will not be able to participate. Immediately following consent and randomization into the "Care Coordination" and "P²E²T²" arms, project staff will assist participants with technology set-up, configuration, use, and ensure that subjects understand the commercial terms of service agreements, before they begin the trial. In order to further protect individual privacy, subjects in the P²E²T² arm may choose to share with their coach only portions of the data streams from their devices/apps. That is, subjects have the option to filter the data streams shared with their coach by time of day, and specific metric (i.e. steps counted, calories burned, etc.).

Variable	Measure	Data Collection		
v ar lable	Measure	Baseline	3 months	9 Months
Age, Gender,	Demographic Data Form	Х		
Race/Ethnicity, Education				
Level, Income Level and				
Insurance Type				
Specific Aim 1				
Focus Groups		Х	Х	Х
Specific Aim 2				
Self-Efficacy	Diabetes Empowerment Scale –	Х	X	Х
	Short Form (DES-SF)			
Readiness to Change	Readiness to Change Survey	Х	Х	Х
Clinical Indicators	Electronic health record	Х	Х	Х
(Abstracted)				
	Patient Health Questionnaire	Х	Х	Х
	depression scale-9 (PHQ-9)			
Quality of Life	Perceived Stress Scale (PSS)	Х	X	Х
Quality of Life	PROMIS Measures – Physical	Х	X	Х
	Function SF, Emotional Distress			
	SF, Sleep Disturbance			

15) Provisions to Monitor the Data to Ensure the Safety of Subjects

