Following consent, participants will be randomized and receive a study identification number. This number will be entered into the secure REDCap database on a tablet. The participant will be offered the questionnaire on either the tablet with their unique study identification shown at top. Their name and other unique identifiers will not be asked during the survey. If the participant would prefer to fill out the survey on paper, the same procedure will be followed and research staff will transcribe the survey into REDCap. Clinical and lifestyle (physical activity, nutrition, sleep) data will be stored in their clinical record (EPIC Hyperspace) which is HIPAA protected. Clinical data in their record may be viewed by their treating physicians and clinical team as part of standard care at UC Davis Health System. Including this lifestyle data in the clinical record will promote a wellness conversation and foster collaboration between diabetes patients and primary care providers.

All data stored by UC Davis researchers will have all personal identifiers removed and labeled with participant's study identification number. All electronic data will be stored on a password protected server that is accessed only by study personnel. All paper data will be stored in locked cabinets in a room with access limited to research personnel.

27) Compensation for Research-Related Injury

This research involves only minimal risk to subjects.

In the event a patient suffers an injury as a result of participating in this research study, the University of California will provide necessary medical treatment. Depending on the circumstances, the costs of the treatment may be covered by University or the study

Patient and Provider Engagement and Empowerment through Technology $(P^2E^2T^2)$ to Improve Health in Diabetes

sponsor or may be billed to the patient's insurance company just like other medical costs. The University and the study sponsor do not normally provide any other form of compensation for injury.

28) Economic Burden to Subjects

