There are no other monetary costs to participate in the study. All technology costs will be covered by the study except if a participant uses their personal smart-phone or computing technology to visualize data collected by the provided activity sensors. This cost is one that the participant was already incurring. If they do not have a personal computing device compatible with the sensor technology, one will be provided without cost for the duration of the study.

29) Consent Process

Patients who are interested to participate in the study or are referred by their primary care provider will receive an initial telephone call to conduct the pre-screening assessment (see attached document) to determine if they are eligible to participate in the study. If someone is determined to be eligible, an appointment will be scheduled to consent the patient. During the consent process, the study will be described to potential participants. A member of the research team will describe the study, what is required of the participant, study procedures and answer any questions the potential participants may have. If the subject would like to take time to consider participation, they will be offered an intake date in the near future.

Following consent using the Informed Consent Document (see attached), subjects are enrolled in the study and randomized into one of two study arms. Subjects will have the choice of receiving a hard copy of their signed consent form or receive the form by email. They will then be administered initial surveys.

A study telephone line is available to allow participants to reach the Project Manager with any concerns regarding ongoing consent or participation.

30) Process to Document Consent in Writing

The research team will follow the "SOP: Informed Consent Process for Research (HRP-090)" (attached) to consent participants.

31) Drugs or Devices

n/a

References

- 1. Dall, TM et al. (2010). The economic burden of diabetes. *Health Affairs* 29:297-303.
- 2. Narayan, KM et al. (2006). Impact of recent increase in incidence on future diabetes burden: U.S., 2005-2050. *Diabetes Care* 29:2114-6
- 3. Boyle, JP et al. (2001). Projection of diabetes burden through 2050: Impact of changing demography and disease prevalence in the U.S. *Diabetes Care* 24:1936-40

Patient and Provider Engagement and Empowerment through Technology $(P^2E^2T^2)$ to Improve Health in Diabetes

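### Baseline questionnaires follow randomisation in a trial with no described blinding, so baseline self-report scores may already reflect the arm

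*Protocol*

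**What the plan says.** The protocol describes the order of intake steps in three places.

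- **Section 29 (Consent Process).** After consent, "subjects are enrolled in the study and randomized into one of two study arms". After a sentence on copies of the consent form comes: "They will then be administered initial surveys".
- **Section 26 (Privacy).** "Following consent, participants will be randomized and receive a study identification number". Then: "The participant will be offered the questionnaire on either the tablet with their unique study identification shown at top".
- **Section 8 (Recruitment Methods).** "This randomization will occur immediately following consent by computer generated randomization programming in Redcap". The study ID is assigned after that. The questionnaires are not placed in this sequence.

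Other sections bear on timing without giving an order relative to randomisation. Section 11 says "At baseline (time of recruitment), all participants will be asked to complete the surveys", and section 14 likewise ties baseline data to recruitment. Section 12 instead places the first questionnaire at the initial orientation. Section 8 (mailed letters) books one appointment for consent and for arm-specific technology training. Section 14 has staff begin technology set-up straight after randomisation. Section 9 gives the device at the start to the intervention arm and on completion to the usual care arm.

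The SAP calculates change from baseline to 3 and to 9 months for the questionnaire scores and compares arms by t test. It also fits mixed models with a group indicator and a group-by-time interaction, and it plans a post-hoc analysis by stage of change at baseline.

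**The concern.** Randomisation makes the arms comparable only on what is measured before allocation can influence it. A person just told that they will, or will not, receive a nurse coach and a sensor may answer questions on confidence, readiness, mood and stress differently. The difference between arms at baseline is then partly an effect of allocation, and subtracting that baseline carries it into the treatment estimate.

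Self-efficacy, the outcome used to size the trial in section 7, is one of these self-reports. The distortion could hide a real effect or create a false one. A larger sample does not remove it, and makes a false difference more likely to reach significance.

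**Working it through.** **1. Does any section put the questionnaires first?** No. Sections 26 and 29 independently give consent, randomisation, questionnaire. The ID also fixes the order: the questionnaire displays the study ID (section 26), and the ID is issued at or after randomisation (sections 8 and 26). As written, the form cannot be offered before randomisation. The recruitment-time wording in sections 11 and 14 fits either order.

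**2. Would the participant know the arm?** The moment of disclosure is not stated. No blinding is described, the arms differ visibly, and training and set-up belong to the same visit. Disclosure before the questionnaire is therefore likely but not documented.

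**3. Could coaching come before baseline?** Section 12 puts the first questionnaire at the initial orientation. In the intervention steps, the technology orientation is listed second, after the first coaching contact. Most of the protocol points to the intake visit, but nothing excludes the other reading.

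**4. How does a shift enter the estimate?** Let δ be the true between-arm difference in change, b the baseline shift (intervention minus usual care) caused by knowing the arm, and k the fraction of b still present at follow-up. Then

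expected contrast = δ + kb − b = δ − (1 − k)b.

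The same holds for the group-by-time terms, since baseline is one of the outcome times.

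**5. Illustration.** The documents give no estimate of b, so there is no figure of theirs to reproduce.

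- From protocol section 7: δ = 4.03 − 3.64 = 0.39; SD 0.70; 150 per arm planned; 100 per arm as the reduced case; 126 = 150 × (1 − 0.16) after the cited attrition.
- From the SAP: two-sided 0.05.
- Assumed: b = ±0.10; baseline/follow-up correlation r = 0.5; k = 0 unless stated. The 0.39 is treated as a difference in change, which follows if true baseline means are equal.

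SD of change = 0.70 × √(2(1 − r)) = 0.70 × √1 = 0.70. The standard error is 0.70 × √(2/n): 0.099, 0.088 and 0.081 at n = 100, 126 and 150. Rejection probabilities come from the noncentral t with noncentrality equal to contrast/SE (for example 0.29/0.099 = 2.93).

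| Case | Contrast | n = 100 | n = 126 | n = 150 |
|---|---|---|---|---|
| True 0.39, no shift | 0.39 | 97.5% | 99.3% | 99.8% |
| True 0.39, b = +0.10 | 0.29 | 83.0% | 90.6% | 94.7% |
| True 0.39, b = −0.10 | 0.49 | 99.9% | >99.9% | >99.9% |
| No effect, b = ±0.10, k = 0 | 0.10 in size | 17.1% | 20.4% | 23.4% |
| No effect, b = ±0.10, k = 0.5 | 0.05 in size | 7.9% | 8.7% | 9.5% |
| No effect, k = 1 | 0 | 5% | 5% | 5% |

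Sensitivity to r, with no effect, a net shift of 0.10 and 126 per arm: r = 0.3 gives a change SD of 0.828 and 15.9% rejection; r = 0.7 gives 0.542 and 30.8%.

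**The case against.** The strongest reply is that prior knowledge of the arm is inferred. Sections 26 and 29 deal with privacy and consent and are not visit schedules. Set-up is described for both arms, so starting it need not reveal the allocation. Sections 11 and 14, which define baseline, tie it to recruitment. That is why the conclusion says the scores may reflect the arm. It does not overturn the order: two sections agree on it, the ID makes it necessary, and nothing safeguards the questionnaire from prior disclosure.

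The magnitude is also hypothetical. The 17% to 23% rejection rates need a 0.10 shift (0.10/0.70 = 0.14 SD) that has vanished by follow-up. Because participants know their arm throughout, some persistence is at least as plausible, and half or full persistence gives 8% to 9% or 5%. Even with b = +0.10, power stays above the 80% that section 7 claims. All of this stands, and the figures show what could happen rather than what to expect.

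The point about coaching before baseline rests only on the order of a list. It stands as an ambiguity in wording to clear up, not as a demonstrated fault.

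Finally, taking baseline before randomisation does not remove open-label reporting bias at follow-up. A persistent shift that cancels under the present order would enter the change score under the new one. That is true. But cancellation depends on the shift being equal at every time point, which cannot be verified. A clean baseline at least confines the problem to the follow-up reports.

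**Conclusion.** The concern holds. Followed as written, the protocol yields post-randomisation baselines for every self-reported outcome, without described blinding, and the SAP builds its treatment contrasts on them. The exploratory stage-of-change analysis uses a baseline with the same weakness. That participants know their arm by then is likely, not stated. The size and direction of any bias are unknown. Under the assumptions above, a 0.10 shift moves the planned 0.39 to 0.29 or 0.49 and lifts the false-positive rate to between 17% and 23%, falling to the nominal 5% as the shift persists. Laboratory values are much less exposed. This should be fixed: it is an avoidable risk to the outcome that sizes the trial, and the remedy is cheap.

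**What to change.** State one order in protocol sections 8, 12, 26 and 29: consent; assignment of study ID; completion of the baseline questionnaires; REDCap randomisation; then disclosure of the arm, orientation and any coaching contact. ID assignment has to move ahead of randomisation because the questionnaire carries the ID. Set REDCap so that randomisation cannot run until the baseline survey is submitted. Reconcile the orientation wording in section 12 with the recruitment wording in sections 11 and 14, so that baseline precedes any coaching contact.

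The cost is a reordering within the same visit, a wording change and a REDCap rule, with no extra visit. Patients who will not complete the 10-15 minute survey would not be randomised, and paper forms would have to be transcribed before randomisation could proceed.

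The protocol expected completion by the end of 2017 and the SAP is dated January 2019, so the order may no longer be changeable. In that case, report the order actually used and when participants learned their arm. Add a sensitivity analysis comparing 3- and 9-month scores between arms without using baseline, which a baseline-only shift cannot bias.

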Patient and Provider Engagement and Empowerment Through Technology Program to Improve Health in Diabetes

PI: [name]

January 11, 2019

NCT number: NCT02672176

Analytical and Statistical approaches

We will use Stata v15.0 (Stata Corp, College Stations Tx 2017) for all statistical analyses. Descriptive analysis will yield means/standard deviations for continuous variables and frequencies for categorical variables. We will examine distributions to determine whether data meets assumptions for planned statistical analyses. We will compare patient demographic and health-related characteristics between the individuals in the intervention group and the usual care group. We will compare continuous variables using a Student's t test or the Wilcoxon Signed-Rank test, and will compare categorical variables using the chi-squared test and Fisher's exact test, as appropriate. We will compare number of steps per week at baseline (Week 2) versus 3 months (Week 13), baseline versus 9 months (Week 37) and 3 months versus 9 months, using a paired t-test to evaluate the change in physical activity over time.

We will calculate change in outcomes over time as the difference between baseline and 3 months, and baseline and 9 months for diabetes self-efficacy scores, depression severity (PHQ-9), patient stress score, and PROMIS measures (Emotional distress anxiety, and physical functioning). We will use Student's t test to compare the change in outcome between usual care and intervention groups (Significance level: $p \le .05$).

In the primary analysis, we will estimate the difference over time in the effects of the intervention over usual care in the study participants. This is an intent to treat analysis, with the assumption that any dropouts are missing at random. We will also use an analytical method (Mixed model) which accounts for the missing data contributed by participants who dropped out from the study. Lastly, we will conduct a sensitivity analysis to determine whether there is a difference with regards to the significance of our findings when we exclude participants who drop out from the analysis. All participants, regardless of intervention completion, will be included in the intent to treat analysis.

We will use multivariate regression modeling for all hypotheses testing to estimate withingroups and across group effects of the intervention on the outcome (significance level: $p \le$ 0.05). The mixed effects models will evaluate the impact of the intervention over time in the outcomes of Diabetes Self-Efficacy, depressive symptoms, and Perceived Stress Score (PSS). We will include a binary indicator for intervention group assignment, and a group- by-time interaction term in the models to compare improvement over time between the intervention group and usual care group. We will assess all variables for collinearity before including in the model. We will evaluate model fit using deviance tests for nested models, the Akaike Information Criterion, and the Bayesian Information Criterion for non-nested models. We will assess the estimates for the fixed effects using a pre-determined significance level (p < 0.05) on two sided tests and 95% confidence intervals. We will use the same approach for analyzing primary and secondary outcomes analyzing the effect of the intervention at baseline, 3 and 9 months.

We will conduct a post-hoc analysis examining the relationship between stage of change at baseline and intervention outcomes. We hypothesize that there might be differences in who the intervention benefits most – and will explores whether readiness to change status might be a tool for screening potential participants for inclusion in future trials or interventions.

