Participants will be recruited from UC Davis Primary Care Clinics, including the Hospital-based clinic and the Folsom Medical Group clinic. After enrollment in the study, participants will be randomized into one of two groups: Care Coordination (usual care) offered through UC Davis Health Management and Education; or the $(P^2 E^2 T^2)$ Program to Improve Health in Diabetes (intervention), which includes nurse coaching paired with sensor technology to provide targeted feedback of patient generated real-world physical activity and sleep quality data to the nurse coach, participants and primary care providers to improve self-management of diabetes. Those randomized to receive the intervention will interact with their coach through mobile technologies by telephone, face-to-face videoconference, or by text/e-mail through EPIC MyChart, the electronic health record system used by UC Davis Health System, that is secure and HIPAA

Patient and Provider Engagement and Empowerment through Technology $(P^2E^2T^2)$ to Improve Health in Diabetes

protected. The secure mHealth dashboard platform (Synopsis) is developed within EPIC Hyperspace for communication and collection of data. The telephone and face-to-face videoconference interactions will be initiated by the nurse coach from a secure location. All other interactions with patient happen within the electronic health record environment which is secure.

Inclusion criteria will be:

 At least 18 years of age
Diagnosis of Diabetes Mellitus (type 2)
Receiving care at one of the UC Davis Primary Care participating clinics (hospital-based Primary Care Clinic, the Folsom Primary Care Clinic)
Able to read, write, and speak English
Has access to a telephone and computing device
Has had experience with use of a mobile smartphone & applications
HgbA1C over 6.5%

1) Does not have Diabetes Mellitus

2) Primary language is not English

3) Pregnant women

4) Those that not have access to a telephone or computing device

5) Has a HgbA1C value under 6.5%

7) Number of Subjects

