13) Data and Specimen Banking

n/a

14) Data Management and Confidentiality

Data will be collected from participants at three time points: 1) baseline data at time of recruitment; 2) 3 months (coinciding with the program completion); and 3) 9 months (selected to assess sustained effects of the intervention). At baseline, in addition to

Patient and Provider Engagement and Empowerment through Technology $(P^2E^2T^2)$ to Improve Health in Diabetes

outcomes described in Table 2, all participants will complete a demographic survey which will include age, gender, race/ethnicity, education level, income level and insurance type and health history using the Charlson Comorbidity Index which includes common chronic conditions. All data for the study will be collected by the research coordinator and entered into the REDCap (Research Electronic Data Capture) system housed in the servers managed by UC Davis Clinical and Translational Science Center (CTSC) (26).

REDCap is a secure, web-based application designed to support data capture for research studies, providing: 1) an intuitive interface for validated data entry; 2) audit trails for tracking data manipulation and export procedures; 3) automated export procedures for seamless data downloads to common statistical packages; and 4) procedures for importing data from external sources. REDCap stores data on a secure server and eliminates any confidential information from being stored on personal computers. Mental health diagnoses and treatment information will be directly entered into the REDCap database by the DHHS Quality Assurance Officer. No materials with confidential information will be removed from the DHHS site.

Nurse health coaching provided to the intervention group will have additional documentation related to the intervention and goal setting within an Epic module built for the project. Progress notes from the nurse health coach interactions will be available for other members of the care team to access when working within a participant's chart. This element is essential as one of our aims is to determine if the presence of patient-generated sensor data and personal health goals within the EHR results in differences in diabetes related outcomes.

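### The SAP names a paired test (Wilcoxon signed-rank) for comparing characteristics between two independent arms; its Week 2 step 'baseline' also needs a clear label

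*SAP*

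**What the plan says.** **Test for characteristics.** The SAP (Analytical and Statistical approaches, first paragraph) says that demographic and health-related characteristics will be compared between the two arms. The next sentence gives the methods. Continuous variables get Student's t test "or the Wilcoxon Signed-Rank test, and will compare categorical variables using the chi-squared test", with Fisher's exact test as the other categorical option. The rank-sum (Mann-Whitney) test is named nowhere in either document.

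**Allocation.** Protocol section 8: "Randomization will be conducted through computer generated randomization using REDCap data management system". This follows each participant's consent. No matching or pairing is described.

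**Steps.** The same SAP paragraph continues: "We will compare number of steps per week at baseline (Week 2) versus 3 months (Week 13"), then "baseline versus 9 months (Week 37) and 3 months versus 9 months, using a paired t-test". The event from which weeks are counted is not given.

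**Protocol time points.** Section 14 lists "1) baseline data at time of recruitment; 2) 3 months (coinciding with the program completion") and a 9-month collection. Section 11 describes the last time point as "data at 6 months after the end of the intervention (9 months after baseline").

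**Who has the technology, and when.**
- Section 6 describes the intervention as a program "which includes nurse coaching paired with sensor technology", and section 12 places the sensor orientation within that program.
- Section 9 gives the intervention arm its device at the start. Usual care gets one only after all questionnaires are complete.
- Section 14 has staff help with technology set-up "Immediately following consent and randomization into the" two arms, both of which it names.
- Section 8 (mailed letters) mentions technology training for either arm.

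**The concern.** The signed-rank test works on differences within pairs. A participant in one arm has no partner in the other, so the planned comparison supplies nothing for the test to act on. An analyst who follows the text literally must invent a pairing, drop people, or depart from the SAP. What is at stake is the p-values in the table of group characteristics, wherever the rank alternative is chosen over the t test.

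The step analysis raises a smaller question of labelling. The word baseline means recruitment in the protocol and Week 2 of sensor data in the SAP. A reader who takes the two as the same would misread what the paired change covers.

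**Working it through.** There is no figure in the plan to reproduce on this point. The check sets the texts side by side and then sizes the consequence.

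**1. Could the signed-rank test belong to a within-person comparison?** No. The sentence that names it follows directly on the announcement of a between-arm comparison. The one explicitly paired comparison, steps, has its own sentence and its own paired t test.

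**2. Unequal arms.** The signed-rank test needs equal numbers. The protocol (section 7) expects at least 150 per arm and at most 350 in total; it does not mention blocking. Assume simple 1:1 randomization of 2 × 150 = 300:
- Probability of exactly 150/150 = C(300,150) / 2^300 = 0.046.
- Mean absolute difference in arm size = 13.8.

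So under that assumption unequal arms are the usual case, and the named test could not use everyone.

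**3. Equal arms, arbitrary pairing.** If both arms share one distribution, the difference between two independent draws is symmetric about zero. A pairing made without regard to the data therefore keeps the nominal error rate. Simulation agrees: 150 per arm, 10,000 datasets per setting, one row-order pairing each, two-sided 0.05. The distributions are assumed.

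| Setting | Rank-sum rejects | Signed-rank rejects | Verdicts differ |
|---|---|---|---|
| Normal, no difference | 5.1% | 5.3% | 2.4% |
| Normal, 0.2 SD | 38.7% | 38.4% | 7.4% |
| Lognormal (log SD 1), no difference | 4.9% | 4.8% | 3.3% |
| Lognormal, 0.2 log units | 39.5% | 35.7% | 11.9% |

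A repeat with other random numbers gave 4.4% to 5.0% with no difference, for both tests.

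The dependence on record order shows in a single simulated dataset (lognormal, 150 per arm, 0.25 log-unit shift). Rank-sum gave p = 0.0026. Over 2,000 arbitrary pairings of the same values, signed-rank p ran from about 0.00003 to 0.020.

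**4. Reach.** The SAP analyses outcomes with Student's t test on change scores between arms and with mixed models that include a group-by-time term. Neither uses the signed-rank test.

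**5. What Week 2 is.** Steps come from the study sensor, which is set up after randomization (protocol sections 9, 12 and 14). A Week 2 value is therefore recorded after set-up, later than the recruitment baseline of section 14. The paired comparisons from it span 13 − 2 = 11 weeks and 37 − 2 = 35 weeks. Any change before Week 2 is in neither. The documents give no step data, so its size is unknown.

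**6. Week numbers.** At four weeks to a month, 3 × 4 = 12 completed weeks, so the next is Week 13; 9 × 4 = 36, so the next is Week 37. The gap is 37 − 13 = 24 = 6 × 4, which agrees with the protocol's six months. The labels fit that count, but neither the rule nor the starting event is stated.

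**The case against.** The strongest reply is that this is a slip of the pen. A statistician would run the rank-sum test, and unequal arms would probably expose the error when the named test could not be run on everyone. Even where it could be run, the simulated false-positive rates are close to 5%, and a saved dataset would reproduce its own p-value. All of that stands, and it is why the point is minor. It does not make the wording right, and correcting it costs nothing.

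On steps, the reply is that the SAP openly writes Week 2 beside the word baseline and never calls it a pre-randomization value. Any sensor reading must follow set-up, and steps are not among the outcomes in protocol section 11 or the measures tabulated in section 14. That also stands. What remains is a difference in the meaning of baseline between the two documents, and a label that resolves it.

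Two stronger readings are tempting and should not be drawn:

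- A reader who converts calendar months to weeks might infer that Weeks 13 and 37 cannot share one origin. They fit a four-week-month count exactly, so the documents show only an unstated rule.
- A reader might infer that the SAP presents the paired step change as an effect of the intervention. It says only that the test evaluates change in physical activity over time, and the paired t test is valid for that.

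**Conclusion.** The test name is wrong as written, with high confidence, because the comparison is between individually randomized, unmatched arms. Severity is minor. The error reaches only the between-arm comparison of characteristics, and only where the rank test is used. It would be too strong to say that it inflates false positives or undermines the outcome analyses. The first is contradicted by the symmetry argument and the simulation; the second by the SAP's own choice of outcome methods. The simulated figures rest on assumed distributions and equal arms of 150. The arm-size figures rest on simple randomization of 300, which the protocol does not state.

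The step point is a clarification. Week 2 is an early on-study reference. That it follows set-up is an inference, but a secure one given the source of the data; how long after set-up it falls cannot be told. Sections 6, 9 and 12 imply that only the intervention arm supplies steps. The SAP does not say so, and sections 8 and 14 leave the position of usual care unclear.

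**What to change.** 1. In the SAP, change the signed-rank test to the Wilcoxon rank-sum (Mann-Whitney) test for comparisons between arms.
2. Label Week 2 steps as an early on-study reference recorded after sensor set-up, and keep the paired t tests.
3. State the event from which weeks are counted and the rule that links Weeks 13 and 37 to 3 and 9 months.
4. State which arm supplies step counts.
5. Reconcile protocol sections 8, 9 and 14 on what technology usual-care participants receive and when.

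The cost is one test name, one label and two or three sentences in the SAP, plus a protocol clarification. No analysis is added and no outcome analysis changes.
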